1.5.5 Phase I Trial of ATLCAR.CD30 for Relapsed/Refractory CD30+ Lymphoma

At Baylor Drs. [name] and [name] recently completed dose escalation in a phase I trial designed to determine if ATLCAR.CD30 was safe for therapy of CD30+ HL and CD30+ NHL and would persist in these subjects long enough to potentially control disease.

ATLCAR.CD30 were given to 9 subjects (7 with HL and 2 with CD30 + ALCL) with relapsed/refractory HL or CD30+ NHL. Eight of the 9 subjects had relapsed or progressed after treatment with brentuximab vedotin. Two were treated on dose level (DL) 1 (2×10^7 CAR-T/m²), two on DL2 (1×10^8) and five on DL3 (2×10^8), without any conditioning regimen before T cell infusion, as mandated by FDA to exclude occurrence of "on target-off tumor" toxicities. CAR-T cell infusions produced no attributable adverse events, and none of the subjects developed a CRS. Nine subjects were evaluable for antitumor responses. At 6 weeks after treatment, 4 subjects had stable disease, 1 had PR and 1 had a CR, while 3 subjects (1 of whom with ALCL) had disease progression [63].

After establishing the safety and persistence of ATLCAR.CD30 in the nontransplant setting, LCCC1524-ATL is designed to determine if these cells are safe for consolidation therapy following autologous transplant and will persist in subjects with CD30+ HL or NHL long enough to potentially control or prevent disease after high dose therapy and ASCT.

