3.2 Secondary

- 3.2.1 PFS is defined from day of ASCT to relapse (in subjects with a documented complete response after ASCT) or progression (in subjects with documented stable disease or partial response after ASCT), or death as a result of any cause as per the Revised Response Criteria for Malignant Lymphoma (see APPENDIX II-Revised Response Criteria for Lymphoma) [74].
- 3.2.2 Overall survival will be measured from the date of administration of CAR.CD30 transduced ATL to date of death.
- 3.2.3 Persistence of CAR.CD30 T cells in vivo will be determined by quantitative PCR and flow cytometry in peripheral blood samples.

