- 6. HIV, HBV, HCV testing required for confirmation that no active infection exists; results can be pending at the time of cell procurement; only those samples confirming lack of active infection will be used to generate transduced cells. Virus testing may be performed up to 30 days prior to procurement.

- 7. See section 8.2, procurement happens after pre-procurement screening and prior to ASCT. Procurement may occur prior to or after PBSC mobilization. If procurement occurs after PBSC mobilization, it must occur at least 7 days after ending use of G-CSF
- 8. Complete Metabolic Panel (CMP): includes BUN, creatinine, Na, K, Cl, CO2, glucose, calcium, albumin, total protein, total bilirubin, ALT, AST, and alkaline phosphatase. NOTE: *Pre-procurement, only creatinine, bilirubin, and AST is necessary, and if these tests have already been performed within 7 days of procurement as part of SOC pre-transplant work-up (i.e. as part of CMP), they do not need to be repeated. Prior to ATLCAR.CD30 treatment, a CMP must be performed within 24 hours prior to infusion. CMP performed as needed on D1/Week 3.
- 9. To assess disease status, imaging will be performed at baseline (within 60 days prior to ASCT) and at 6-8 weeks following the infusion. The choice of imaging will depend on what studies have been most informative in following the subject's disease (i.e., PET, CT scans, MRI, nuclear imaging). In subjects who do not have documented disease progression at the 6 weeks scan, another scan will occur at 6 months, 12 months, 18 months and 24 months (with a +/- 1 month window), until documentation of disease progression. If imaging studies are performed at other times after treatment on this study; that data will be collected, and information gained will be used for this study.

Response assessment for subjects with cutaneous T cell lymphoma

- a. Will be performed at the same time point outlined above in the Time and Events Table and by the few exceptions outlined in section 7.1.1.
- b. Notable differences in the follow up for these subjects are outlined in section 7.1.1 based on consensus guidelines.
- c. Consult with a dermatologist will be required within 14 days prior to transplant.
 - 10. Thyroid function (T3, Free T4 and TSH) will be monitored in view of changes seen in subjects receiving CD30 antibody.

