 - 15. ATLCAR.CD30 cells infused after evidence of hematologic recovery post ASCT, see section 4.1.2 for definition of recovery. This will generally occur between 14 and 20 days following infusion of autologous stem cells following high-dose chemotherapy. All subjects will receive their ATLCAR.CD30 infusion at the lead site, the University of North Carolina, Chapel Hill.
 - 16. Patient reported outcomes (PRO) will be measured by the PROMIS Global Health and Physical Function questionnaires and selected items from the NCI PRO-CTCAE (see section 7.6 and APPENDIX V - Patient Reported Outcomes Surveys) (optional). PRO questionnaires will only be offered to adult study participants. PRO questionnaires will first be given at time of screening consent. On the day of infusion, subjects will fill out questionnaires prior to infusion. These questionnaires are optional and may not be given to all subjects.
 - 17. Long Term Follow Up: If a subject develops a delayed adverse event that is related to the trial drug, then more frequent (2-4 times per year) clinical observation may be indicated. Appropriate follow up will be conducted based on a particular subject's prior test results. The investigator will determine the additional testing and sample collection that is needed. New malignancies and delayed adverse events will be recorded during long term follow-up.

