5.2 Inclusion Criteria Prior to Infusion of ATLCAR.CD30 Cells

- 1. Informed consent explained to, understood by and signed by subject/guardian; subject/guardian given copy of informed consent.
- 2. 3 to 17 years of age for pediatric subjects, ≥18 years of age for adults; NOTE: children will not be allowed to enroll in a dose cohort until a minimum of 2 adult subjects were enrolled and complete their DLT assessment follow-up at that dose level.
- 3. Diagnosis of recurrent HL with a treatment plan that will include high dose chemotherapy with/without total body irradiation and autologous cell transplantation.
- 4. NHL subjects with ALK negative CD30+ anaplastic large-cell lymphomas, CD30+ ALCL regardless of ALK status, with chemotherapy-sensitive relapse, CD30+ highrisk DLBCL, CD30+ cutaneous T cell lymphoma, or CD30+ mycosis fungoides who are otherwise eligible for transplant, are eligible for this study.
- 5. CD30+ disease (result can be pending at the time of cell procurement, but must be confirmed prior to treatment with ATLCAR.CD30 cells); NOTE: CD30+ disease requires documented CD30 expression by immunohistochemistry based on the institutional hematopathology standard.
- 6. Evidence of adequate organ function as defined by:

The following is required prior to infusion of ATLCAR.CD30 cells:

• Absolute neutrophil count (ANC) ≥500 cells/mm3 for 3 consecutive days; Note: ANC may be measured at the beginning and the end of a time frame expanding at least 3 days and does not need to be evaluated on each individual day **AND**

- Platelet count ≥25,000 cells/mm3 without transfusion over preceding 5 days; Note: Platelets may be measured at the beginning and the end of a time frame expanding at least 5 days and does not need to be evaluated on each individual day **AND**
- Hg \geq 8g/dL without transfusion support over preceding 5 days; Note: Hg may be measured at the beginning and the end of a time frame expanding at least 5 days and does not need to be evaluated on each individual day
- Bilirubin ≤ 1.5 times the upper limit of normal (ULN)
- AST \leq 3 times ULN
- Serum creatinine ≤1.5 times ULN
- Pulse oximetry of > 90% on room air
- 7. Imaging results from within 60 days prior to transplant (used as baseline measure for documentation of disease status).
- 8. In women of child-bearing potential (WOCBP), a negative serum pregnancy test within 72 hours prior to procurement and again 72 hours prior to infusion is required.

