7.2.2 Pre-infusion

Check eligibility

Clinical evaluation: History, physical examination, Karnofsky or Lansky performance status

Laboratory studies:

- Pregnancy Test: serum pregnancy testing will be done in female subjects of childbearing potential (within 72 hours prior to infusion)
- Pulse Oximetry
- CBC with differential and platelets: (required within 24 hours prior to infusion)
- CMP: (required within 24 hours prior to infusion) BUN, creatinine, Na, K, Cl, CO2, glucose, calcium, albumin, total protein, total bilirubin, ALT, AST, alkaline phosphatase
- Thyroid function: obtained pre-infusion
- Dermatology consult needed for cutaneous lymphomas only
- Blood taken for leukemia profile and flow cytometry (mycosis fungiodes and Sezary syndrome patients only)
- Blood Sample for Correlative Studies (see section 7.5)
 - Function and persistence studies: Including in vitro reactivation of PBMCs in subjects for whom the appropriate reagents are available and immunophenotyping
 - Replication competent retrovirus (RCR): Sample collected preinfusion for PCR testing
 - Quantitative PCR
 - HAMA testing
 - Cytokine testing: obtained pre and post infusion

Toxicity: Toxicity will be assessed according to the NCI CTCAE v. 4.0.

CoA: Generated at completion of required studies for production/QA of cell (available prior to planned infusion)

Patient reported outcome questionnaires for adult subjects (optional): PROMIS Global Health Scale, PROMIS Physical Function, and selected questions from NCI PRO-CTCAE. This will be collected on the day of infusion prior to infusion.

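### Read literally, section 3.2.1 does not count progression found at or before the first post-transplant scan as a PFS event in subjects assessed by imaging

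*Combined protocol and SAP*

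**What the plan says.** Section 3.2.1, repeated in the Study Summary, starts the clock at transplant and gives three routes to an event. The first is relapse: "PFS is defined from day of ASCT to relapse (in subjects with a documented complete response after ASCT"). The other two are "progression (in subjects with documented stable disease or partial response after ASCT), or death as a result of any cause". Section 3.2.1 refers to Appendix II for the response criteria. Section 11.3.4 adds only that PFS is as defined in 3.2.1 and will be estimated by Kaplan-Meier.

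Footnote 9 of the Time & Events Table (section 4.2) sets the imaging schedule: "imaging will be performed at baseline (within 60 days prior to ASCT) and at 6-8 weeks following the infusion". Criterion 7 of section 5.2 takes the disease-status baseline from before transplant: "Imaging results from within 60 days prior to transplant (used as baseline measure for documentation of disease status"). The pre-infusion visit in section 7.2.2 lists "Clinical evaluation: History, physical examination, Karnofsky or Lansky performance status" and laboratory work, but no tumor imaging. Footnote 15 times the infusion: "This will generally occur between 14 and 20 days following infusion of autologous stem cells following high-dose chemotherapy".

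Footnote 9 also foresees progression at the first scan: "In subjects who do not have documented disease progression at the 6 weeks scan, another scan will occur at 6 months", followed by scans at 12, 18 and 24 months.

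**The concern.** Each non-fatal route to an event carries a condition: a disease status documented after ASCT. For subjects followed by imaging (HL, systemic ALCL, DLBCL, and cutaneous cases followed by scans), the schedule does not produce that status before the first post-infusion scan. If that scan shows progression, the subject has no post-ASCT CR, PR or SD on record and meets neither condition. The same holds for a subject who progresses clinically before the scan. Progression between ASCT and infusion is not among the exclusions in section 5.3 and has no route either.

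The subjects left out are the earliest treatment failures, so any error goes one way: PFS looks better than it is. PFS is a named secondary objective (2.2.2), and in a trial of 12-18 subjects one or two such cases visibly move the curve.

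**Working it through.** The documents give no PFS sample size, event count or target, so there is no stated figure to reproduce. The check compares the definition with the schedule and then scales the effect.

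**1. When the first post-ASCT scan falls.** Infusion is generally 14-20 days after ASCT (footnote 15). The scan is 6-8 weeks, or 42-56 days, after infusion (footnote 9).
- Earliest: 14 + 42 = 56 days after ASCT.
- Latest: 20 + 56 = 76 days after ASCT.

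**2. Whether a status can be documented before then.**

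| Point in time | What is scheduled | Can it document CR, PR or SD after ASCT by imaging? |
|---|---|---|
| Up to 60 days before ASCT | Baseline imaging | No, it precedes ASCT |
| Pre-infusion | History, physical exam, performance status, laboratory tests | No imaging |
| Weeks 1, 2, 3 (optional), 4 | History, physical exam, laboratory tests | No imaging |
| 6-8 weeks after infusion | First post-ASCT scan | Yes, unless it shows progression |

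**3. Whether a later rule repairs it.** Section 11.3.4 has no event or censoring rule beyond 3.2.1. Section 4.1.4 lets subjects with progressive disease receive other therapy. Once they do, Appendix IV schedules history, performance status, correlative samples and survival, but no imaging. After progression at the first scan, the only route left in the definition is death.

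**4. How many subjects.** The documents give no early progression rate for this population. The closest benchmark is in section 1.4: a median PFS of 24.1 months on placebo after ASCT in high-risk HL. Assume a constant hazard, a clock comparable to this trial's, and 30.44 days per month. The probability of progression or death by day t is then 1 − 0.5^(t / median).
- Day 56: 56 / 30.44 = 1.84 months; 1 − 0.5^(1.84 / 24.1) = 0.05.
- Day 76: 76 / 30.44 = 2.50 months; 1 − 0.5^(2.50 / 24.1) = 0.07.
- In 18 subjects: 18 × 0.05 = 0.9 to 18 × 0.07 = 1.3, so about 1.

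This includes deaths, which 3.2.1 does count, and it describes HL only. If the chance of progression by the first scan were 10% or 20% (assumed values), the expected number would be 1.8 or 3.6 of 18. The probability of at least one such subject is 0.60 at 5%, 0.85 at 10% and 0.98 at 20% for N=18. For N=12 it is 0.46, 0.72 and 0.93.

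**5. Effect on the curve.** Let k subjects progress by the first scan, with no other event or censoring before it. If they are counted, the Kaplan-Meier estimate just after the scan is (N − k)/N. If not, it is 1.000. If they are censored at that scan, every later estimate is multiplied by N/(N − k).

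| N | k | Counted | Not counted | Later inflation if censored |
|---|---|---|---|---|
| 18 | 1 | 0.944 | 1.000 | 1.06 |
| 18 | 2 | 0.889 | 1.000 | 1.13 |
| 18 | 4 | 0.778 | 1.000 | 1.29 |
| 12 | 1 | 0.917 | 1.000 | 1.09 |
| 12 | 2 | 0.833 | 1.000 | 1.20 |

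Each uncounted subject raises the curve at the first scan by 1/18 = 0.06, or 1/12 = 0.08 at the smaller size.

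**The case against.** The strongest reply is that the rest of the protocol already treats progression at the first scan as progression. Footnote 9 reserves further scheduled scans for subjects without it. Section 7.8 runs imaging until progression is documented. Appendix II judges progressive disease against baseline or nadir and asks for no earlier response. On that view the parentheses only explain vocabulary: relapse follows a complete response, and progression is the term otherwise. If the analyst reads them so, there is no bias, and nothing in the documents says that early progressors will be censored or dropped. This stands as evidence of intent. It does not change the wording: Appendix II says how progression is recognised, while 3.2.1 says in whom it counts.

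A reader might infer that nothing at all is assessed between ASCT and the first scan, or that the curve cannot fall before the second post-infusion scan except by death. The documents do not support either. Physical exams are scheduled pre-infusion and at weeks 1, 2, 3 (optional), 4 and 6. For cutaneous lymphoma with negative baseline scans, section 7.1.1 makes the skin exam the response assessment. Section 7.2.2 lists a pre-infusion dermatology consult for cutaneous disease, and blood flow cytometry for mycosis fungoides and Sézary syndrome. Unscheduled scans after treatment are collected and used (footnote 9, section 7.8) and could document a status early. Such subjects may escape the problem, but unscheduled scans are not required, so classification would then depend on local practice.

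A reader might also take the earlier CAR.CD30 trial in section 1.5.5, where 6-week results included six subjects with stable disease or better "while 3 subjects (1 of whom with ALCL) had disease progression", as a sign that a third of subjects would be affected. That cohort was 9 relapsed/refractory subjects treated outside the transplant setting, 8 of them after failure of brentuximab vedotin and all without conditioning. It is not a usable rate for consolidation after ASCT.

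**Conclusion.** The definition is wrong as written, and the matter is minor. For imaging-assessed subjects, 3.2.1 and the Study Summary require a documented post-ASCT status that the schedule cannot supply before the first post-infusion scan. They thereby conflict with footnote 9 and Appendix II. The upward bias arises only if the text is applied literally; the documents do not show that the sponsor means to leave early progressors out.

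The size is uncertain. About 1 of 18 subjects would be affected if the 24.1-month placebo median carries over with a constant hazard. That figure covers HL only and includes deaths; the number would be larger if early progression is commoner in this population. PFS is descriptive here, with no hypothesis test or decision rule, and dose assignment, the CRM and the MTD do not depend on it.

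**What to change.** In section 3.2.1 and the Study Summary, delete the two parenthetical conditions. Define the PFS event as the first documented relapse or progression after ASCT, or death from any cause, whether or not a CR, PR or SD was documented after ASCT. State that relapse or progression is judged by Appendix II, VI or VII according to histology, against the pre-ASCT baseline or the later nadir.

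Section 11.3.4 points to 3.2.1 and will follow. The change rewords one definition in two places and needs no extra scan or visit. Its only downside for the sponsor is that the reported PFS may be slightly less favourable.

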3.3 Exploratory

This study is a multicenter, open-label phase I clinical trial testing the hypothesis that the administration of ATLCAR.CD30 to subjects with CD30+ lymphoma post autologous transplant is safe as evidenced by the rate of DLT. The rate of DLT will be used to determine the MTD; see section 4.1.3.2. Three dose levels of ATLCAR.CD30 will be evaluated to determine a recommended dose in adult and pediatric subjects. Initially, only adults will be enrolled during the dose escalation phase of the study. Once a dose level has been tested in at least 2 adults without the occurrence of DLTs during the assessment period, children may then be enrolled on that dose level according to the CRM. Each subject will receive one injection followed by close monitoring over the subsequent 6 weeks. See section 7.4 for schedule of longer term follow-up.

Subjects scheduled to undergo an ASCT at one of the protocol sites for treatment of lymphoma will be approached for consent to screening and potential enrollment into LCCC1524-ATL. Peripheral blood cells will be collected from consenting subjects who meet eligibility for cell procurement for creation of ATLCAR.CD30 cells (see section 4.1.1) prior to ASCT. The ASCT, including mobilization and collection of PBSCs, administration of myeloablative therapy, reinfusion of PBSCs and supportive care following transplant will be as per routine standard of care, and not expected to be impacted by enrollment into LCCC1524-ATL. Post ASCT, subjects who meet eligibility criteria for treatment will receive one infusion of ATLCAR.CD30 cells once there is evidence of hematologic recovery as defined in section 4.1.2. Research personnel will keep track of any subjects who undergo procurement but do not undergo treatment with ATLCAR.CD30 cells, and the reason for withholding treatment.

4.1 Study Treatment

4.1.1 Cell Procurement

In adult subjects, up to 300 mL total of peripheral blood will be obtained (in up to 3 collections) for cell procurement. In pediatric subjects, up to 3 mL/kg of peripheral blood will be obtained (in up to 3 collections) for cell procurement Additionally, leukopheresis leukapheresis may be performed to isolate sufficient cells in subjects with a low absolute lymphocyte count or who had inadequate peripheral blood collection.

For pediatric patients (patients under 18 years of age), the total amount of blood drawn will not be more than 3 mL (less than 1 teaspoon) per 2.2 lbs. that the child weighs.

4.1.2 ATLCAR.CD30 Cells Administration

Post ASCT, once the subject has started to experience hematologic recovery (defined as ANC \geq 500 cells/mm3 for 3 consecutive days, AND platelet count \geq 25

cells/mm3 without transfusion over the preceding 5 days, AND Hg \geq 8g/dL without transfusion support over preceding 5 days), ATLCAR.CD30 cells will be administered as described below. The dose of cells and exact day of cell infusion will vary, depending on the cohort enrolled. See section 4.1.3 for dose levels and dose escalation rules. This will generally occur between 14 and 20 days following infusion of autologous stem cells following high-dose chemotherapy.

Premedication

Subjects may be pre-medicated with Benadryl (diphenhydramine) up to 1 mg/kg IV (max 50mg) and Tylenol (acetaminophen) 10 mg/kg oral (max 650mg). Alternative antihistamines or anti-pyretics can be used in the case of diphenhydramine or acetaminophen hypersensitivity. We will premedicate subjects who have a history of reactions to blood products. Steroids should be avoided given their detrimental effect on the survival of the infused T cells (see exclusion criteria 5). Anti-emetics in appropriate dosage for each subject will be prescribed as necessary.

Cell Administration

ATLCAR.CD30 cells will be given by a licensed provider via intravenous injection over 1-10 minutes through either a peripheral or a central line. The expected volume will be 1-50cc.

Monitoring

Monitoring will be undertaken according to institutional standards for administration of blood products. Subjects will be monitored for at least 4 hours post infusion.

4.1.3 Dose Escalation Rules

Three dose levels will be evaluated. Using the continual reassessment method (CRM), initial cohort of size two will be enrolled at each dose level (see section 11.), after that subjects are enrolled one at a time until a minimum of 12 subjects is treated. Each subject will receive one injection according to the dosing schedules listed below. We will start with the lowest cell dose $(2 \times 10^7 \text{ cells/m}^2)$ given to subjects in one of our previous trials employing CAR-T cells including the CD28 costimulatory endodomain [26], and we will escalate the cell dose to the highest cell dose $(2 \times 10^8/\text{m}^2)$ given in the same trial [26]. These are also the doses utilized in the phase I trial using ATLCAR.CD30 and described in section 1.5.5. All those

cell doses were safe. A maximum dose is included for each dose cohort in order to avoid excessive dosing secondary to obesity and potentially resulting in toxicity. The maximum dose is calculated based on a body surface area of 2.5 m^2 .

Note: Initially, only adults will be enrolled during the dose escalation phase of the study. Once a dose level has been tested in at least 2 adults without the occurrence of DLTs, children may then be enrolled on that dose level according to the CRM.

Cell dose Levels

Table 1 Group One

Schedule	ATLCAR.CD30 ²	Maximum Dose				
Week 0 Day 11	$2x10^7$ cells/m ²	5x10 ⁷ cells				

Table 2 Group Two

Schedule	ATLCAR.CD30 ²	Maximum Dose				
Week 0 Day 11	$1 x 10^8$ cells/m ²	2.5x10 ⁸ cells				

Table 3 Group Three

Schedule	ATLCAR.CD30 ²	Maximum Dose			
Week 0 Day 11	$2x10^8$ cells/m ²	5x10 ⁸ cells			

The dose is based on the CAR.CD30 expressing cell. With a lower limit of CAR positivity at 15%, even a larger subject (2.0 m^2) would receive 2.66×10^9 total cells which would still be in the lower range of infused cells as reported by Johnson *et al.* [75].

- 1. Only one infusion will be administered, and will be given after stem cell transplantation and engraftment as defined in section 4.1.2.
- 2. If there are insufficient cells manufactured for a subject to receive their proposed dose level, the subject may be infused with a quantity of cells consistent with one of the previously cleared dose levels.

Definition of MTD

For this study, MTD is defined as the dose that causes DLT (see section 4.1.3.3) in 10% of eligible cases. The trial will continue until a minimum of 12 subjects is treated. Six additional subjects might be accrued to obtain more data at the current MTD. The final MTD will be the dose with estimated probability of the DLT closest to the target toxicity rate of 10%.

Definition of a DLT

The timeframe for DLT evaluation is from day of infusion through 6 weeks post infusion.

Except as noted below, DLT will be defined as any of the following that may, after consultation with the FDA, be considered possibly, probably, or definitely related to the study cellular products:

- Grade 3 and 4 cytokine release syndrome (CRS*) that persists beyond 72 hours, or any Grade 5 CRS
- Any other ≥ Grade 3 non- hematologic toxicity, including allergic reactions to T cell infusions

*Grade 3 and 4 expected CRS reactions seen with the use of CAR-based immunotherapy such as (but not limited to) fever and hypotension requiring pressor support will not be considered a DLT unless it persists beyond 72 hours.

CRS toxicity will be graded according to the toxicity scale outlined in section 18.8 (APPENDIX VIII- CRS Toxicity Grading Scale and Management Guidelines).

Supportive Care

Subjects will receive supportive care for acute or chronic toxicity, including blood components or antibiotics, and other intervention as appropriate.

